stored in the travel case. In the long-term, an accelerometer will also be integrated to measure the gyration and jaw motion. **Firmware.** A software program will be developed to capture pure analog data captured by the sensor, analyze the data, correlate them to a force level, and provide reliable outputs. The software will also include a data transfer method using Bluetooth Low Energy (BLE), power management for battery charging and management, as well as accelerometer data collection and processing. It most likely will be developed in C or C++ depending on the microcontroller being used. **Validation & Data Analysis.** A test jig will be developed to replicate bite compression motions under a wide range of compression forces by simulating patients with no/mild and moderate/severe bruxism (average maximum bite compression forces is around 500 N). The test jig design would consist of a force testing machine coupled with a mechanical model of the patient's mouth. The completed bruxism sensor would be placed on the model to calibrate the FSR to the applied force. Otis/Brash anticipates the end-product will require patients to perform a pre-calibration step to measure the absolute forces at the beginning of each session before data is collected during sleep. To replicate this step, Brash will calibrate the sensor by using known test mass standards comparable (e.g., 0, 0.1, 0.5, 1, 2, 10 kg) typical loading forces in the jaw. After calibration, the test jig will be programmed to capture force linear loading and unloading force profiles with a range of loading rates (e.g., 1 min to maximum force down to 1s to maximum force). A root mean squared error will be calculated to compare the reference force and measured force by the test jig. The result will provide an initial validation that the measurements are accurate within the force and inform Brash how the accuracy might be affected by the loading rates. Brash will also compare loading and unloading errors since FSR sensors have known hysteresis, likely resulting in a larger error in unloading force profiles. Repeatability will also be examined by programming a repeated force profile over a full measurement cycle of 8 hours. This step is critical as repeatability will be the principal metric of interest as it allows for comparative analysis to determine if a user's bruxism is improving or worsening over time. To verify the repeatability and hysteresis of the Brux-sensor, the calibration will first be validated by applying a gradually increasing linear force ramp up at varying rates (e.g., 10, 50, 100N/s). A full 8-hour test will also be pursued to simulate the sleep time period.

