**Aim 3: Conduct a usability pilot study with 28 patients to capture bite compression force profiles and optimize data collection.** Otis will determine whether the OBSNG prototype can reliably capture bite compression force data with participants. In summary, Otis will screen and recruit 28 participants (50/50 Male/Female; 14 with no/mild bruxism and 14 with moderate/severe bruxism) to wear the Otis Brux-Sensor Night Guard prototype for 21 days over a 6+ hour sleep period each night. [name] (lead PI) is a licensed dental hygienist with over 13 years of performing oral health screenings and will train each patient on how to use the device and perform the calibration step before each participant begins the study. Otis/Brash will confirm that the prototype can store the data, transmit it to the software, and analyze the data. Brash will analyze the data collected to determine whether the patient's jaw forces can be analyzed and replicate similar compression forces from the jig. Using this data, Brash/Otis will evaluate whether a trend difference can be identified between patients with no/mild bruxism compared to participants with moderate/severe bruxism. Brash/Otis will also evaluate whether the core functionality of the technology can measure forces while using the device to ensure measurements are repeatable within reasonable deviance. The study protocol will be reviewed and approved by an internal review board (IRB) (TBD).

**Procedure: Screening/recruitment:** Otis will recruit 28 participants to meet our recruitment criteria from the Otis Dental customer database. For recruitment, [name] will reach out via email to all Otis Dental customers who are currently wearing the Otis Custom Night Guard, and advertise an opportunity to be part of the study. All interested participants will reply to [name], who will then send them more information providing an overview and scope of the pilot study. Participants will fill out a screening survey to ensure they are willing to wear a custom night guard for 3 weeks (21 days), undergo an initial tele-dental health screening by [name] (licensed dental hygienist) before participating in the study, and have data collected from the sensor-enhanced custom night guard. Demographic background information (e.g., age, gender, race, health history, etc.) will also be collected at this time. To meet the eligibility criteria, participants must have access to a smartphone, be fluent English-speaking,

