Participants with Moderate/Severe Bruxism	Moderate-to-severe physical wear on anterior teeth and/or posterior molars; moderate-to-severe clicking/popping and/or misalignment of the jaw joint; moderate-to-severe gum recession; Reported stress levels to be moderate/high	The night guard shows significant wear after 1 week of use.	Compression forces between 100-200N

**Procedure:** Each participant that meets the screening criteria and is eligible to participate in the study will meet with [name] to receive a prototype of the OBSNG. [name] will provide both written and verbal instructions on how to use the OBSNG. [name] and [name] will also calibrate the device before first use by candidates, followed by another calibration, after the last use by the candidate. This will allow the team to determine any potential data discrepancies due to gradual wear throughout the utilization of the device. All participants will be asked to wear the Otis Brux-Sensor Night Guard before going to bed for 21 consecutive days. Here, participants will be instructed to (1) take the Otis Brux-Sensor Night Guard out of the storage case; (2) seat the device on their upper dentition; (3) sleep with the device on for a minimum of 6 hours; (4) clean the night guard with a tepid water rinse, after each use; (5) place the night guard back into the storage case and allow to air dry for next use). All who complete the study will be compensated with a \$100 Visa Gift card and they can keep the custom night guard (retail value of up to \$500). **Data analysis:** The team will begin averaging all compression force episodes throughout each of the 6+ hours of sleep per night and graph all 21 nights of averaged scores to show every candidate's Bruxism pattern during the study. The team will determine the bruxism severity (no/mild or mod/severe), based on the range of compression forces and validate each candidate's bruxism severity.

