**Milestone:** > 90% of the prototypes can store data for the 21-day trial throughout the 6+ hour sleep period and transmit the data to the software; moderate/high bruxism participants having averaged compression forces 100 - 200 N) greater than the average compression bite force profiles to that of the no/mild bruxism participants (or 25-50% greater); agreement between oral assessment, physical nightguard wear, and compression forces according to **Table 1**; confirm reproducibility and accuracy of data collection by checking daily variability of bruxism patterns from both groups to determine if severe bruxer values (100 – 200 N compression force) are consistently higher than mild bruxers values (25 - 100 N of compression force), from night-to-night.

**Problems and Solutions:** If the sensor becomes damaged due to saliva and/or water cleaning, various dental adhesive materials will be tested to protect the sensor from damage, without jeopardizing nocturnal function.

**Statistics.** Upon Phase I completion, Otis will pursue a Phase II proposal to further optimize the prototype via a larger clinical study by analyzing varying severity levels of bruxism using statistical means and AI/ML techniques.

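### The Aim 3 milestone on reproducibility and accuracy is decided by whether severe bruxers read higher than mild bruxers, which measures group separation and neither property of the sensor

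*Protocol*

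**What the plan says.** All places are in Protocol section 3.2.

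- **Aim 3, Milestone.** One of the four milestones is to "confirm reproducibility and accuracy of data collection by checking daily variability of bruxism patterns from both groups". The check is whether severe values (given as 100 to 200 N) "are consistently higher than mild bruxers values (25 - 100 N of compression force), from night-to-night". The milestone does not say whether group means or individuals are compared or on how many nights the ordering must hold, and it gives no tolerance.
- **Aim 3, design.** There are 28 participants, "14 with no/mild bruxism and 14 with moderate/severe bruxism". Each is asked to "wear the Otis Brux-Sensor Night Guard before going to bed for 21 consecutive days". Force episodes are averaged within each night, and the team will "graph all 21 nights of averaged scores to show every candidate's Bruxism pattern during the study".
- **Aim 3, summary.** A further aim is to "ensure measurements are repeatable within reasonable deviance", with no figure attached.
- **Aim 3, Procedure.** The device is calibrated before first use and again after last use, to pick up discrepancies from wear. The milestone does not use these calibrations.
- **Aim 1, Validation & Data Analysis.** On the bench, accuracy is error against a known force: "A root mean squared error will be calculated to compare the reference force and measured force by the test jig". Repeatability is tested with a repeated force profile over 8 hours. The text adds that "repeatability will be the principal metric of interest", because it shows whether one user is getting better or worse.
- **Aim 1, Milestone.** The accuracy margin is 10% to 15%.

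**The concern.** Accuracy is closeness to a true force. Reproducibility is agreement of repeated readings under like conditions. The milestone names both and then decides them by asking which of two groups of people reads higher. A poor sensor meets that rule when the groups are far apart, and a perfect sensor fails it when they are close.

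This is not detail left to a statistical analysis plan, because the protocol itself fixes the criterion. It also departs from the protocol's own bench definitions. Phase I is meant to deliver a working prototype for Phase II, so an imprecise device could be carried forward as reproducible and accurate, or a sound one marked down, on the property that Aim 1 ranks first.

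**Working it through.** The protocol gives no error rate, standard deviation or within-person correlation for this milestone, so there is no figure of its own to reproduce. Assumptions are marked as such.

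**1. Named property against deciding rule**

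| | Aim 1 (bench) | Aim 3 milestone |
|---|---|---|
| Accuracy | Root mean squared error against reference force; 10% to 15% margin | Severe higher than mild |
| Repeatability | Same force profile repeated over 8 hours | Severe higher than mild, night to night |
| Reference force | Yes | None during sleep |

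This comparison needs no assumption, and the main point rests on it.

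**2. Do poor sensors pass?** The rule is read as severe-group mean above mild-group mean on all 21 nights, 14 per group. Assumed: true group means of 62.5 N = (25+100)/2 and 150 N = (100+200)/2, between-person SD 18 and 25 N, night-to-night SD 15 N. Reading = gain × true force + noise.

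| Sensor | RMSE as share of mean force | Passes |
|---|---|---|
| Perfect | 0% | 100% |
| Reads 40% low | 44% | 100% |
| 30% device-to-device gain error + 40 N noise | about 50% | 99.9% |
| 50% gain error + 60 N noise | about 79% | about 95% |

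The last three miss a 10% to 15% margin by a wide distance and still pass.

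**3. Does a perfect sensor pass?** Total variance is set to 1 and ICC is the between-person share (assumed). With no true group difference it passes in about 5% (ICC 0.5) to 27% (ICC 0.9) of studies. With a true difference of 0.5 SD it passes in about 50% to 78%. Passing therefore follows group separation more than sensor quality.

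**4. Secondary: passing by chance.** The same 14 and 14 people supply every night, so a chance imbalance between the groups recurs. With no true difference, the group difference is D ~ N(0, 2·ICC/14) and nightly error is N(0, 2·(1−ICC)/14). Then

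P(all 21 nights) = ∫ Φ(z·√(ICC/(1−ICC)))²¹ φ(z) dz.

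At ICC 0.5 this is exactly 1/22 = 4.5%.

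| Reading of the rule | ICC 0.3 | 0.5 | 0.7 | 0.8 | 0.9 |
|---|---|---|---|---|---|
| Group means, all 21 nights | 1% | 5% | 12% | 18% | 27% |
| Group means, at least 19 of 21 | 6% | 14% | 23% | 28% | 35% |
| Ranges bind: severe mean ≥ 100 N and mild mean ≤ 100 N, all 21 nights | – | 0.2% | 1.5% | 3% | 7% |

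The third row takes a common true mean of 100 N, the value easiest to pass. The two groups are independent and each must stay on its own side of 100 N, so the first-row probability is squared: 0.0455² = 0.002, 0.121² = 0.015, 0.180² = 0.032, 0.268² = 0.072. If every severe participant had to exceed every mild participant, the chance is at most 1/C(28,14), about 2.5 × 10⁻⁸.

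**5. Calibration range.** The largest example mass in Aim 1 is 10 kg, and 10 × 9.81 = 98 N. That lies just below the 100 to 200 N band expected for the moderate/severe group.

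**The case against.** **The device is checked elsewhere.** Aim 1 has bench accuracy and repeatability tests, Aim 3 plans calibration before and after use, and patient forces are to be compared with those from the jig. The sentence ranking repeatability first belongs to the bench work. This stands, and a reader should not infer that the plan has no check on the sensor. It does not repair the Aim 3 milestone, which uses none of these.

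**The chance argument is easily overstated.** A reader might infer that the milestone is readily met by luck, or that 28 × 21 = 588 nights are being counted as independent. The documents support neither. No planned test, standard error or interval treats the nights as independent, and nightly averages are graphed per participant. The chance figures also fall sharply if the newton ranges bind, and vanish if individuals must be ordered. Groups are assigned on tooth wear, joint signs, stress and guard wear, so exactly equal mean force is not the likeliest state. All of this stands, and chance remains a secondary point.

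**Binding ranges would catch some bad sensors.** If they bind, a sensor reading 40% low could fail, so that result holds for the ordering rule alone. Even then, the ranges are anticipated group values and not reference measurements.

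**Night-to-night variation is no clean substitute.** It mixes real changes in bruxism with sensor error, so a perfect sensor on a variable bruxer looks poor. This stands and shapes the fix.

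**Conclusion.** The point holds as a mismatch between what the milestone claims and what it measures. Ordering two groups confirms neither accuracy nor reproducibility, under any reading of the rule and without any assumed correlation. The size of the mismatch, with sensors about 44% to 79% in error passing in about 95% to 100% of studies, rests on the Table 1 midpoints, the assumed SDs and the group-mean reading.

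The chance figures (about 5% to 27%, or at most about 0.2% to 7% with binding ranges) depend on the reading and on an ICC that the protocol does not give. They should not carry the argument.

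This should be fixed, but it is not a fatal flaw: it is one of four milestones in a 28-person usability pilot, and statistical discrimination of severity is deferred to Phase II.

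**What to change.** Replace the milestone with separate statements.

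1. **Accuracy and drift.** At the planned post-use calibration, record the unadjusted reading against known reference forces before any re-zeroing or rescaling. Report percent error relative to the pre-use calibration and judge it by the Aim 1 margin of 10% to 15%. The pre-use calibration cannot serve alone, because it is the step that sets the device. State the force range covered, since example masses ending at about 98 N do not reach the 100 to 200 N band.
2. **Reproducibility.** Report within-participant night-to-night variation (coefficient of variation, ICC) descriptively, labelled as biological plus sensor variation. Rest the claim of sensor repeatability on pre- to post-use calibration drift and the bench repeat profile.
3. **Group separation.** Make it a milestone of its own: one 21-night mean per participant, 14 versus 14, difference with a 95% confidence interval.
4. **Deletion.** Remove the night-to-night group ordering as evidence of reproducibility or accuracy.

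The cost is protocol wording and a small change to the analysis. The nightly forces and both calibrations are already planned, so no new data are needed.
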